Inpatients waiting for cardiac surgery are well monitored. Being admitted to hospital forces a person to accept that they have a problem that need sorting out. This should make them a receptive audience to our intervention. If exercise is proven possible in this population, this will open the opportunity for larger studies to ascertain its benefit and safety. Once safety is known in this population, this may then encourage a wider acceptance of prehabilitation for all population.

Whilst we are unable to incorporate nutrition into our study, we still firmly believe there is a role for nutrition in prehabilitation. However, in the acute setting, this will be limited in the form of advice and information. The education will need to be continued post operatively to consolidate the knowledge for patients.

Deterioration in mental health is associated with increased mortality after cardiac surgery.²⁶ Despite this, mental health has remained a taboo topic up until recently. The younger population maybe more comfortable talking about emotions and seeking help. However, the cardiac surgery population are generally older and it is not clear if they will take up the psychological intervention offered.

Cardiac surgery is a tertiary service which means that patients could live hundreds of miles from the closest centre. Larger studies need to demonstrate the benefits of prehabilitation (if any) for the patients and hospitals. Once the benefits and safety of prehabilitation is established, there is a need to have prehabilitation centres that are easily accessible to patients to reduce care inequality. The centralisation of service also leads to increased strain on the tertiary services. As a result, the waiting times for both elective and urgent cardiac surgery have increased over the years.¹ This waiting time is unlikely to resolve soon enough. Whilst waiting, patients should be working on improving their general health and well being. Surgery should not be viewed as an end point but an opportunity to improve their general wellbeing.

References:

1. National Institute for Cardiac Outcomes Research. National Adult Cardiac surgery audit 2017-2020.2021.

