This single centre, prospective, pilot feasibility trial will recruit 20 inpatients awaiting cardiac surgery. Measurements will be taken at the start of the trial, 7 days after intervention, and 14 days after the intervention or before the day of surgery. The primary outcome measure will be feasibility and practicality of the programme in acute inpatient population. We will be looking into participant eligibility, acceptability, recruitment rates, completion rates and barriers to implementing a prehabilitation programme. Secondary outcomes include safety (incidence of adverse events directly related to the study), improvement in 6 minutes walk test (6MWT), hand grip strength, quality of life, anxiety scores and spirometry. At the end of the trial, we will be seeking the feedback of the participants to help us improve the design further.

Ethics and dissemination

Trial Registration number

Introduction

According to the National Adult Cardiac Surgery Audit (NACSA) over 30,000 heart surgeries are performed every year in the UK.¹ With the increased life expectancy in the UK, the number of heart surgeries is unlikely to reduce. Advancing age is often associated with frailty; a physiological state of diminished response to stressors due to decreased reserve secondary to multiple comorbidities and homeostatic dysregulation.² Accordingly, it is unsurprising that frail patients have poorer outcomes following an illness and incur a higher healthcare cost. There is evidence that frailty is a reversible condition with an improvement of diet, and exercise.³ A randomised control trial found a combination of resistance training and nutritional supplement led to not only an increase in muscle bulk and strength but also improved mobility.³ The possibility of reversing or slowing down this medical condition has led to a lot of interest in the subject.

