Potential participants for the pilot study will be identified from the cardiology team on the ward and acute admission board in the hospital. The cardiology team will give an indication that the patient is likely for surgery and any language barrier. For the purposes of this pilot, only patients that present directly to CHH and able to communicate in English will be considered. Initial screening for the patient will be done by the research team upon speaking to the cardiology team. Eligible participants will be approached by a member of the research team, provided verbal information and following that given the patient information leaflet. They will then be allowed some time to go through the information. The researcher will then return to ask if they would like to participate and consent them if they agree. Once consented, participants will be asked to perform the baseline test. Interventions will begin soon after this. Interventions will be delivered as a mix of information leaflet, face to face session and online video. Surgery and post-operative hospitalisation will take place in the same hospital.

Objective

Primary objective

The primary objective is to determine the feasibility of a prehabilitation program in acute in patient population. We will be looking at the eligibility rates, enrolment/ recruitment rates, practicality of a prehabilitation program in terms of logistical challenges to developing and implementing the program (deliverability), uptake rates, acceptability and completion rates of an inpatient prehabilitation program.

Secondary objective

Secondary objectives are to identify any changes in 6-MWT, hand grip strength, quality of life, spirometry and mental health before and after the program. We will be collecting information on adverse events, length of stay, complication(s) and readmission during this study. This will give us signals for safety concerns and potential efficacy of the program.

Eligibility criteria

Inclusion criteria

All patients over the age of 18 scheduled for acute cardiac surgery will be given consideration to participate in this clinical trial.

Exclusion criteria

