Safety of exercise has not been assessed in this group of patients. To ensure safety of participants, the interventions will be done within the cardiology and cardiac surgery department area in Castle Hill. This enables the participant to have access to round the clock medical and surgical care. The exercise will be stopped if the patient develops symptoms such as angina (chest pain, or pain radiating down the left arm), arrhythmias or any syncopal symptoms. If the symptoms do not improve with rest, they will receive appropriate medical treatment. The exercise will then be stepped down in a gradual fashion with the minimum expectation of resistance exercise only. Participants who cannot perform at least resistance only exercise will be withdrawn from the study and the surgeons will be informed.

We anticipate that the most intense intervention in this study will be the aerobic exercise. As such, it will only be performed under 1:1 direct supervision. Participants who are able to perform the aerobic exercise will only exercise until they achieve their target heart rate. If the target heart rate is exceeded, the intensity of the exercise will be reduced. If however, they are unable to achieve their target heart rate, we will reduce the intensity of the exercise to a level that is acceptable for them. At any stage of the intervention, if the patient develop symptoms as described above, the intervention will be stopped, they will be assessed and treated by the medical team in the same hospital.

We anticipate some patients with cardiac conditions may experience symptoms of postural hypotension which may impact their ability to perform the test. If this occurs, it will be documented by the assessor and patients are told to rest before trying the test again. If they are unable to perform the test at all, they will be withdrawn from the study. We will record adverse and serious adverse events.

In the event that the patient develop evidence of worsening cardiac condition either related or unrelated to the intervention, they will be assessed by the medical team and treated appropriately either with alteration of medication or possibly have the surgery expedited. The decision for treatment options lie with the medical team directly involved in the patient's care. The researchers will not influence the decision regarding the patient's treatment.

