We will be sending out questionnaires pertaining to the patient's mental health. Patient's that score highly or show any features of mental health problem that could impact their safety will either be asked to self refer for help or be contacted by a clinical psychologist. The intervention offered will depend on the severity of condition.

Outcome measures

The primary outcome is the feasibility and acceptability of the multimodal program. Feedback will be obtained from the patient regarding the acceptability, achievability and general interest in the program.

Feasibility will be assessed by determining the number of eligible patients, participants recruited, participated and retained at the end of the intervention, the proportion of intervention sessions delivered and fidelity of delivery. Moreover, participant recruitment, retention and adherence to the intervention will be measured, as well as any adverse events.

To determine the acceptability of the intervention and to explore barriers and enablers to the implementation of the intervention, interviews will be conducted amongst participants, and staff involved in referral and intervention delivery.

Secondary objectives:

- To identify a signal of efficacy for positive changes in physical health exercise, mental wellbeing, and quality of life (using tools described);
- To identify differences in length of hospital stay, complications and readmission rates to hospital following surgery compared to usual care (based on previously collected data);
- Indications of safety concerns with prehabilitation in acute inpatient population. This is based on reported adverse events

The 6 minute walk test, hand grip, quality of life measure, spirometry and cardiac anxiety score will be measured at three points, before the intervention, day 7 and day 14 or before the surgery. If the surgery happens before day 7, there will only be two measurements. Information on any cardiac symptoms and their association with the exercise will be documented.

The end of the trial is defined as the day of surgery for the last participant. Participants may choose to withdraw at any point of the trial. If they are changes in circumstances which would impact their ability to complete the trial, they will be withdrawn by the clinician.

Statistical method

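### The abstract limits the safety outcome to adverse events directly related to the study, while the body of the protocol sets no such limit

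*Protocol*

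**What the plan says.** The protocol describes safety in several places, and they do not agree on which events count.

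- **Abstract, Methods and analysis.** The wording is "safety (incidence of adverse events directly related to the study". This is the only place that attaches a summary measure (incidence) to safety, and the measure is limited to related events.
- **Objective, Secondary objective.** "We will be collecting information on adverse events, length of stay, complication(s) and readmission during this study". The section says this information will give safety signals. It sets no relatedness condition.
- **Safety.** "We will record adverse and serious adverse events". Again there is no relatedness condition. The same section states: "Safety of exercise has not been assessed in this group of patients".
- **Outcome measures.** Adverse events of any kind are measured as part of feasibility. Of the secondary objective on safety concerns, the section says: "This is based on reported adverse events". It also has cardiac symptoms, and whether they were associated with the exercise, documented.
- **Baseline data collection.** The aim is to find safety concerns connected with the programme, using the patient diary and staff notes. This states an aim and gives no counting rule.
- **Statistical method.** Length of stay, complications and readmission are named for analysis. Adverse events are not mentioned, so this section does not settle the question.

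**The concern.** The same data can give two different safety results, depending on which sentence is followed. A protocol should not leave that choice open until the events are known.

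The narrower definition is the weaker one for this trial. The Introduction's part on exercise explains that a faster heart rate in ischaemic disease can bring on angina or myocardial ischaemia. The Safety section lists angina, arrhythmias and syncopal symptoms as reasons to stop exercise. Patients waiting for cardiac surgery can have all of these from their disease alone. No concurrent control group is described. The comparison in Outcome measures, "following surgery compared to usual care (based on previously collected data", covers length of stay, complications and readmission but not adverse events. The protocol names no assessor, criteria or time window for direct relatedness. An event that might be due either to exercise or to disease is the kind a safety signal would consist of, and it is also the kind that a related-only count could leave out.

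**Working it through.** The protocol states no adverse event rate, attribution rate or safety calculation, so there is no figure to reproduce. The contradiction is shown by comparing the sections and needs no arithmetic.

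| Place in protocol | What it governs | Relatedness condition? |
|---|---|---|
| Abstract, Methods and analysis | Outcome and its measure (incidence) | Yes |
| Secondary objective | Collection, as safety signals | No |
| Safety | Recording of adverse and serious adverse events | No |
| Outcome measures | Basis of the safety objective | No |
| Baseline data collection | Aim of identifying concerns tied to the programme | Aim only |
| Statistical method | Adverse events not mentioned | Silent |

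The abstract and Outcome measures both speak to the outcome, and they differ on the numerator. The two remaining sections without a condition concern collection and recording, and they show that the data for the wider count would exist.

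**Illustration of the mechanism (the rates are assumed).**

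Inputs:
- n = 20, from the abstract ("pilot feasibility trial will recruit 20 inpatients awaiting cardiac surgery").
- p = a participant's true risk of at least one adverse event before surgery. Assumed, 5% to 30%.
- f = the chance that an affected participant has an event judged directly related. Assumed, 10% to 100%. f = 100% gives the same result as counting all events.

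Formula, with participants independent: P(no events reported) = (1 − p·f)^20.

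Worked case: p = 0.10.
- All events counted: (1 − 0.10)^20 = 0.122.
- Related events only, f = 0.25: (1 − 0.025)^20 = 0.603.

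| p | f = 100% | f = 50% | f = 25% | f = 10% |
|---|---|---|---|---|
| 5% | 36% | 60% | 78% | 90% |
| 10% | 12% | 36% | 60% | 82% |
| 20% | 1% | 12% | 36% | 67% |
| 30% | 0.1% | 4% | 21% | 54% |

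Even a count of zero in 20 would exclude little. The exact two-sided 95% upper limit is 1 − 0.025^(1/20) = 16.8%, and the one-sided limit is 1 − 0.05^(1/20) = 13.9%. If the count is of related events only, that limit applies to related events and says nothing about the risk of any adverse event.

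The table shows that the two definitions can part company in a trial of this size. It does not show by how much they would differ here.

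**The case against.** The strongest reply is that the relatedness condition is a parenthesis in an abstract and that the body overrides it. Outcome measures is the section meant to define outcomes, and it bases safety on reported adverse events without a filter. Cardiac symptoms are captured through the diary and staff notes whatever their cause, and their association with exercise is documented, which is close to a sub-classification already. Safety is a secondary outcome of a 20-patient feasibility study, and no hypothesis test or progression rule in the protocol rests on it. Denominators, interval methods and table layout can properly be left to a statistical analysis plan.

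Most of this stands. It shows that the abstract is the outlier and that the data for a full count would be available. It does not remove the contradiction. Outcome measures gives a basis for the safety objective but no measure, and the one measure in the protocol carries the restriction.

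A reader might go further and infer that the trial as a whole counts only related events, and so could report almost no harm by putting events down to the disease. The documents do not support that. The restriction appears in the abstract alone, and the body allows all-cause reporting. How events would be attributed is not described, so any prediction about it is conjecture.

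**Conclusion.** The point holds as an internal contradiction: the abstract defines safety by related events only, and three sections of the body collect, record or rely on adverse events without that condition. This rests on the text alone and on no assumed rate.

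The consequence is conditional. If the abstract's definition were used, ambiguous cardiac events could be left out of the safety result of an uncontrolled trial whose own protocol says the safety of exercise is untested in these patients. The size is unknown, because the documents give neither an event rate nor an attribution rate. The tabulated chances depend on the assumed p and f and on independence between participants. They show that the effect is possible and are not an estimate of it. The contradiction should be corrected, but it does not undermine the primary feasibility aim.

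**What to change.** Reword the safety outcome in the abstract to match the Safety and Outcome measures sections: the incidence of all reported adverse and serious adverse events. Report relatedness, and the association with exercise that Outcome measures already documents for cardiac symptoms, as a sub-classification of that total and not as a condition for being counted.

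The cost is one sentence of wording and a slightly less favourable event count. No new adverse event collection is needed, because the Safety section already has adverse and serious adverse events recorded.

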The discipline of physiology teaches us that coronary blood flow is determined by coronary perfusion pressure, perfusion time and vessel wall diameter. In patients without heart conditions, blood flow is auto regulated according to the individual's requirement at a certain point in time. However, in disease states, auto regulation is affected. For instance, in patients with ischaemic heart disease, the coronary arteries are narrowed. A shortening of perfusion time (diastole), as would happen when the heart rate increases, will lead to reduction and possibly obliteration of coronary blood flow. This will in turn lead to chest pain (angina) or even precipitate myocardial ischaemia (MI). Despite this, exercise interventions have been shown to be safe and beneficial in elective patients awaiting CABG.^{13, 14} Despite the concept of prehabilitation being around for many years, there is no standard approach to what constitutes effective prehabilitation. There is unclear evidence as to the type of exercise that confers the highest benefit. Various combinations of aerobic,^{14, 15, 16} flexibility,¹⁴ strength/ resistance training,¹⁵ inspiratory muscle training.¹⁵ Regardless of exercise type, none of the studies reported any increase in adverse events due to exercise in elective patients. To date, there are no published trials looking at the feasibility, safety or benefits of exercise on inpatients awaiting cardiac surgery. There is concerns that physical exertion may induce symptoms or lead to adverse events in inpatient cardiac surgery population. However, there is evidence that 45 minutes per day of resistance training improved muscle strength, size, and mobility without causing adverse event in frail, elderly population.³ According to World Health Organisation, global life expectancy increased by > 6 years but healthy life expectancy increased only 5 years between 2000-2019. In addition, COVID-19 has negatively impacted on population health. The impact of COVID-19 has been attributed to deconditioning, muscle atrophy and decreased exercise capacity.¹⁷ A Delphi study conducted by the WHO reported that the most common post-COVID symptoms included tiredness, breathlessness, and worsening daily function.¹⁸ Frailty is associated with muscle wasting, loss of endurance, decreased balance and mobility, slowed performance, relative inactivity. All these symptoms, are associated with patients requiring cardiac surgery.

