Patients who are unable or unwilling to participate in any of the elements of prehabilitation will be excluded. These include those that have cognitive disability (including unconsciousness), cardiac or clinical instability, functional or anatomical impairment which impairs ability to participate, language barrier or patient refusal. Any language barrier will be identified by the primary clinical team and communicated to the research team. These patients will be excluded as we do not have the translating facility for the purposes of this study. Patients that have impending surgery within 72 hours of arrival to hospital will be excluded. Patients who are awaiting surgery in district hospitals or outside of Castle Hill Hospital will be excluded. A non-exhaustive list of exclusion criteria is included below.

Cardiac/ clinical instability such as:

- Recurrent unstable angina/ crescendo angina
- Untreated decompensated heart failure
- Malignant arrhythmias awaiting treatment
- Resting tachycardia (HR>100 bpm)
- Left ventricular outflow obstruction such as Aortic Stenosis with pre-syncopal or syncopal symptoms
- Unresolved acute pericarditis or myocarditis
- Second or third degree heart block without pacemaker
- Aortic Dissection
- Myxoma

Functional/ anatomical impairment such as:

- Severe musculoskeletal conditions that would prohibit exercise
- Amputees
- Registered blind

Patient recruitment and screening

Patients will be identified on admission via the acute admission board and during multi-disciplinary team (MDT) meeting. All acute patients waiting for cardiac surgery in CHH will be eligible to participate in the survey. As such, they will be approached, given information and invited to do so by a member of the research team.

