Patients that are unable to use the exercise bikes will be asked to walk or use the arm crank as an alternative exercise. Both these activities will be tailored to the individual ability.

Regardless of the type of aerobic exercise, the aim would be to achieve a target heart rate for each patient (40%-50% heart rate reserve). During the exercise, their heart rate will be recorded every minute alongside the corresponding exercise wattage. RPE will be recorded at the end of each session.

Resistance/ strength exercise

Patients will be given the option of an in hospital application (Physiotech) or pictorial and written information on how to perform resistance exercise by their bedside. The physiotech application is currently in use by the hospital physiotherapy team for other surgeries such as orthopaedic. However, this application has not been used in cardiac surgery. The physiotherapy team will be tailoring the exercise for the patients and setting the appropriate recommended targets. The application will require basic data on age, weight and height. The exercises will be using single-use resistance bands. Participants are encouraged to perform the exercise as often as possible with the aim of achieving at least 2 session per week.

Patients who are unable to perform the aerobic exercise (eg due to physical limitation or symptoms) will be asked to perform resistance exercise only. The frequency of exercise will be individualised according to patient's ability and fitness level.

Inspiratory muscle training

Patients at high risk of respiratory complications are given spiroball after the surgery for inspiratory muscle training. As part of the prehabilitation, patients will be given spiroball before the surgery and taught how to use it. The importance of inspiratory muscle training will be explained. Patient can access spiroball training on the physiotech application. The target will be for patients to do 3 sets (consisting of 6 breath each), 5 times a day. Preoperative training should also aid better post operative compliance.

Worry

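### Aerobic intensity is steered by a heart rate target that works badly in an eligible patient whose heart rate does not track effort, and RPE 11 is recorded too late in the session to take its place

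*Protocol*

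**What the plan says.** The Aerobic exercise subsection of the protocol's Intervention section gives two handles on intensity. It first aims for light-to-moderate effort pegged to Borg RPE 11. It then adds a heart rate target covering bike, walking and arm crank: "Regardless of the type of aerobic exercise, the aim would be to achieve a target heart rate for each patient (40%-50% heart rate reserve". Heart rate and wattage are logged each minute; RPE is logged once, when the session ends.

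The Safety section turns the heart rate target into operating rules:

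- End point: "Participants who are able to perform the aerobic exercise will only exercise until they achieve their target heart rate".
- Ceiling: "If the target heart rate is exceeded, the intensity of the exercise will be reduced".
- Target not reached: for those "unable to achieve their target heart rate, we will reduce the intensity of the exercise to a level that is acceptable for them".

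RPE is not mentioned in that section. Separately, exercise stops for angina, arrhythmia or syncopal symptoms whatever the heart rate, and aerobic work is always supervised one-to-one. The Aerobic exercise subsection adds ECG/heart rate monitoring throughout.

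On eligibility, the Exclusion criteria remove "Second or third degree heart block without pacemaker", so a patient whose block is already paced is not removed by that item.

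**The concern.** A heart rate target controls intensity only if heart rate rises with work. In a patient paced at a fixed rate, or with a strongly blunted response, it does not. The end point is then never met and the ceiling never crossed. What remains is the rule for an unmet target. It does not distinguish a patient who cannot work harder from one who is working hard while the heart rate stays put, and it gives no measure of what level is acceptable. It also does not say how long a patient keeps trying before being judged unable to reach the target.

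Two opposite errors are possible: too much effort while an unreachable number is still the aim, and too little once intensity is cut because of the number alone. This matters because the protocol says "Safety of exercise has not been assessed in this group of patients", and safety signals and deliverability of the programme are among the things the pilot is meant to report.

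**Working it through.** The plan has no derived figure to reproduce: 40%-50% is a prescription. The check sets the rules side by side and then asks when they stop acting.

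**1. Rules applied to a patient with a fixed heart rate**

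| Rule | Trigger | Acts? |
|---|---|---|
| End point (Safety) | target reached | No |
| Ceiling (Safety) | target passed | No |
| Target unreachable (Safety) | judgement that it cannot be reached | Yes, downward, with no effort measure |
| Symptom stop (Safety) | angina, arrhythmia, syncopal symptoms | Yes |
| RPE 11 (Aerobic exercise) | patient's rating | Recorded only after the session |

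Wattage is also logged, but no rule uses it, and walking has no obvious wattage reading.

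**2. Why the target cannot be met**

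Target = rest + f × (maximum − rest), with f from 0.40 to 0.50. With any positive assumed reserve, the lower edge lies above the resting rate, so a rate that cannot rise never reaches it. Illustration with assumed values (not in the protocol) of rest 60-80 and maximum 140-160 bpm:

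- Lowest target: 60 + 0.4 × (140 − 60) = 92 bpm.
- Highest target: 80 + 0.5 × (160 − 80) = 120 bpm.

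A patient fixed at 60-80 bpm reaches none of these.

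**3. Blunted rather than fixed response**

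Let R be the assumed reserve and e the number of bpm by which the attainable maximum falls short of the assumed one. True reserve is R − e.

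- Ceiling cannot be exceeded when R − e ≤ 0.5R, that is e ≥ 0.5R.
- Target unreachable when R − e < 0.4R, that is e > 0.6R.
- Band as a share of true reserve: 0.4R/(R − e) to 0.5R/(R − e).

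The rest/maximum pairs are assumed. All resting values are admissible, since the exclusion is "Resting tachycardia (HR>100 bpm" and so bars only rates above 100.

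| Rest/maximum | R | Band (bpm) | Ceiling off at e ≥ | Unreachable at e > | Band as % of true reserve, e = 10 |
|---|---|---|---|---|---|
| 90/140 | 50 | 110-115 | 25 | 30 | 20/40 to 25/40 = 50.0-62.5% |
| 75/150 | 75 | 105-112.5 | 37.5 | 45 | 30/65 to 37.5/65 = 46.2-57.7% |
| 60/160 | 100 | 100-110 | 50 | 60 | 40/90 to 50/90 = 44.4-55.6% |

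At e = 10 the ceiling is 0.5 × 10 = 5 bpm too high, a modest shift. Only a large shortfall, or a fixed rate (R − e = 0), switches the rules off.

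**4. Timing of RPE**

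The exercise alternates one moderate and one low minute. If a session lasts 10-20 minutes (assumed), it has 10/2 = 5 to 20/2 = 10 moderate minutes. The single rating comes after all of them, so as recorded it cannot guide any of them.

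**The case against.** The strongest reply is that the affected patient already has a written rule and that it errs downward: when the target cannot be reached, intensity is cut, not raised. The symptom stop works at any heart rate, and an exercise physiologist is present throughout. RPE 11 is the stated basis of intensity and is nowhere withdrawn; a rule on when to record it does not stop the supervisor asking during exercise. The exclusion list is described as not exhaustive, so some paced patients may be screened out in any case.

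Most of this stands, and it rules out several stronger readings that a reader might infer:

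- *Nothing limits effort in a paced patient.* Not supported. The unmet-target rule and the symptom stop both act.
- *The protocol's own coronary-flow warning applies to this patient.* Not supported. The Prehabilitation- Exercise section describes shortened perfusion time, "as would happen when the heart rate increases, will lead to reduction and possibly obliteration of coronary blood flow". With a fixed rate the heart rate does not rise.
- *Missing the target sends the patient down to resistance exercise or out of the study.* Not supported. That step-down follows symptoms; a missed target leads only to lower intensity.
- *RPE 11 and 40%-50% of reserve contradict each other.* The document does not show this. They can apply together.
- *Not saying how the maximum heart rate is obtained is itself an error.* That is missing operating detail, as is the recording of rate-limiting drugs.

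What the reply does not remove is that the unmet-target rule waits on an unguided judgement and then cuts intensity whatever the actual effort. RPE 11 could guide that judgement, but the rule does not refer to it.

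**Conclusion.** The point holds in a narrow form. The Safety rules steer aerobic intensity by a heart rate target that, in an eligible patient whose heart rate does not track effort, cannot serve as end point or ceiling. The remaining heart rate rule lowers the dose without measuring effort. The likely result is a dose somewhat too high before the judgement or too low after it, with the harm limited by supervision, monitoring and the symptom rules.

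The size cannot be fixed from the document. The number affected among 20 is unknown and may be zero. The heart rates and session length used above are assumptions, the behaviour of heart rate under pacing is general clinical reasoning, and the eligibility of paced patients is inferred from one exclusion item. This is a cheap improvement of low severity, not a flaw that threatens the trial.

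**What to change.** Make two changes of wording.

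1. In Aerobic exercise: take RPE during the moderate intervals as well as at the end of the session.
2. In Safety: where the clinical team judges heart rate an unreliable guide to effort, RPE 11 governs intensity in place of the heart rate target, and intensity is not reduced solely because the target has not been reached.

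Leave the symptom stopping rules unchanged for everyone.

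No extra staff or equipment is needed, since the supervisor is already present and heart rate is already logged each minute. The downside is more ratings: at one per moderate minute in an assumed 10-20 minute session, 5-10 extra, so 6-11 in total instead of 1.
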